13.0 DATA AND SAFETY MONITORING

The NEI Serious Adverse Event (SAE) Review Committee is responsible for monitoring data and safety and will exercise oversight of the clinical investigation independently from the study investigators.

13.1 Coordinating Center

The Emmes Company, LLC has been assigned as the coordinating center for this trial to conduct data collection, protocol monitoring, data analysis and reporting. The coordinating center provides routine monitoring of study participants' data. Monitoring visits will occur on a schedule depending on the status of the study. More frequent monitoring visits will be performed at the beginning of the study when enrollment is open. Monitoring will decrease as enrollment closes and as participant follow-up continues.

Although Emmes advises the NEI Clinical Director and Principal Investigator on data and statistical activities, the coordinating center staff does not have direct access to or interaction with participants.

13.2 NEI Adverse Event Review Committee

The NEI SAE Review Committee, which consists of the NEI Clinical Director and three other NEI physicians, will be responsible for reviewing any reported serious safety events, if they occur under this protocol. The Committee will review accumulating data on a semiannual basis to determine whether the study should continue. The study PI will recuse herself from discussions of this

protocol. If changes to the protocol are indicated, recommendations will be made to the NEI Director and Institutional Review Board (IRB) who will consider and act on such recommendations in a timely manner. Should any suspected serious adverse reactions occur, the NEI Clinical Director may, at his discretion, assemble the Review Committee before the scheduled date to consider if the study should go forward. In addition, if three or more participants experience non-serious suspected adverse reactions that require temporary or permanent cessation of the IP, the PI shall report this to the NEI Clinical Director. The NEI Clinical Director may convene the Review Committee before the scheduled time to consider the cessation of the study as a whole.

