4.3 Study Design and Procedures

The study duration will be three months for the first cohort during which participants will be instructed to take vitamin A palmitate 16,000 IU daily by mouth for two months. In the second cohort, the study duration will be two months and the participants will be instructed to take vitamin A palmitate 48,000 IU daily by mouth for one month. In addition, there will be a screening visit between 60 days and one day prior to the baseline visit. For the first cohort, the primary outcome will be assessed at baseline versus Month 2 and the secondary outcomes will be assessed at baseline versus Month 2 and baseline versus Month 3. For the second cohort, the primary outcomes will be assessed at baseline versus Month 1 and the secondary outcomes will be assessed at baseline versus Month 1 and baseline versus Month 2. For both cohorts, visits will occur at baseline, and then monthly and as clinically indicated. The study will require five visits for the first cohort and four visits for the second cohort. All visits must be conducted within a window of \pm 14 days from the target day. At each visit, the participant will undergo a review of systems, such as an assessment of headache frequency and severity, as well as an assessment of safety variables. The tests scheduled at each visit may be split and completed within seven days (including the 7th day) from the visit date. A complete ophthalmologic examination will be performed at each visit to measure outcome variables. Participants will be screened with serum for hepatitis or hepatic dysfunction. However, for caution, we will monitor liver function tests. If participants in either cohort cannot tolerate the prescribed dose of vitamin A palmitate, they will be instructed to stop taking the supplement and they will be removed from the study.

If participants are on Coumadin® (Warfarin) at enrollment, they must visit their prescribing physician to check their Coumadin® status within two to four weeks after initiating IP to have their

Coumadin® regimen adjusted if necessary (as taking vitamin A and Coumadin® can increase the chances of bruising and bleeding.)

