13.3 Criteria for Stopping the Study

The NEI SAE Review Committee may recommend temporarily suspending or closing enrollment or stopping the study at any time due to safety concerns, demonstration of efficacy or lack of efficacy or slow recruitment.

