APPENDIX 2: STUDY FLOWSHEET

Study Visit ⁷	Screening	Baseline	Month 1	Month 2	Month 3 ⁸
Visit Number	-001	000	001	002	003
Target Day from Baseline Visit	-60 to -1	0	30	60	90
Visit Window	N/A	N/A	-14 days/ +14 days	-14 days/ +14 days	-14 days/ +14 days
Cohort 1: Treatment					
Vitamin A palmitate 16,000 IU dispensed		X	X		
Cohort 2: Treatment					
Vitamin A palmitate 48,000 IU dispensed		X			
General Assessments					
Medical/ Ophthalmic History	X	X			
Supplement Accountability			X	X ⁹	
Concomitant Medications Assessment	X	X	X	X	X
Adverse Event Assessment			X	X	X
Review of Systems		X	X	X	X
Ophthalmic Assessments					
BCVA (ETDRS) ¹	X ¹	X	X	X	X
Manifest Refraction ²		X		X	
Slit Lamp Examination	X	X	X	X	X
Dilated Fundus Examination	X	X	X	X	X
Intraocular Pressure (IOP)	X	X	X	X	X
Color Fundus Photography [†]		X		X	X
AdaptDx dark adaptation testing	X ⁴	X	X	X	X
Medmont dark adaptation testing	X ⁴	X	X	X	X
Fundus Autofluorescence ^{†3}		X		X	X
Optical Coherence Tomography (OCT)	X	X	X	X	X
Low Luminance Questionnaire (LLQ)		X	X	X	X
Low Luminance Visual Acuity (LLVA)		X	X	X	X
Laboratory Assessment					
Hepatitis Screening (HCV Ab and HBsAg)	X ⁵				
Hepatic panel (checks liver function testing)	X ⁵		X	X	X
Serum Vitamin A levels	X ⁵		X	X	X
Pregnancy Test	X ⁶	X	X	X	X

† The color fundus photography and fundus autofluorescence results may be utilized from any NEI protocol if performed within six months of baseline.

¹ The option to use the BCVA (ETDRS) short testing can only occur during the screening visit. The BCVA (ETDRS) full testing will occur at the baseline and subsequent visits

² BCVA with manifest refraction must also be performed when scheduled and when there is a change in visual acuity of ≥ 10 ETDRS letters (≥ 0.20 logMAR) from the last study visit.

³ Fundus Autofluorescence may include multi-spectral imaging.

⁴ If AdaptDx and/or Medmont have been performed within 6 months under any other protocol, they do not have to be done at the screening visit. For participants who have exceeded the AdaptDx test ceiling during any NEI protocol, their data will be accepted regardless of their test date.

⁵ Screening labs can be performed under this protocol or another NEI protocol (08-EI-0102, 11-EI-0147, 16-EI-0134, 17-EI-0112, or 16-EI-0024) within 60 days of projected baseline visit.

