3.0 GENERAL REVIEW OF STUDY DESIGN

3.1 Study Design

The DA VitA AMD study is a prospective, uncontrolled, single center, pilot study to investigate the potential efficacy and safety of vitamin A palmitate dosing in improving dark adaptation in participants with AMD (without RPD) and abnormal dark adaptation.

The study will require five visits (screening, baseline, Month 1, Month 2, and Month 3) for Cohort 1 and four visits (screening, baseline, Month 1, and Month 2) for Cohort 2. Participants in Cohort 1 will be instructed to take vitamin A palmitate 16,000 IU daily by mouth for two months from baseline through Month 2 and will continue in the study through Month 3. Participants in Cohort 2 will be instructed to take 48,000 IU of vitamin A palmitate daily by mouth from baseline through Month 1 and will continue in the study through Month 2. The screening visit must occur between 60 days and one day prior to the baseline visit while Months 1, 2 and 3 visits must be conducted within a window of \pm 14 days from the target day. The tests scheduled at each visit may be split and completed within seven days (including the 7th day) from the visit date. At each visit, the participant will undergo a review of systems, such as an assessment of headache frequency and

severity, as well as an assessment of safety variables. A complete ophthalmologic examination will be performed at each visit to measure outcome variables. If participants in either cohort cannot tolerate the prescribed dose of vitamin A palmitate, they will be instructed to stop taking the supplement and they will be removed from the study.

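### On Cohort 2's planned schedule, non-serious toxicity first found at the scheduled post-dose visits would not meet the Section 13.2 count, because the count requires cessation of the supplement

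*Protocol*

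**What the plan says.** Protocol 13.2 sets out three routes to the NEI SAE Review Committee.

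- Routine: "The Committee will review accumulating data on a semiannual basis to determine whether the study should continue".
- Serious events: "Should any suspected serious adverse reactions occur, the NEI Clinical Director may, at his discretion, assemble the Review Committee before the scheduled date".
- Non-serious events: the principal investigator must report to the Clinical Director "if three or more participants experience non-serious suspected adverse reactions that require temporary or permanent cessation of the IP". The Clinical Director may then convene the committee early.

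Section 13.3 adds that the committee may recommend "stopping the study at any time due to safety concerns", with no number attached.

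On Cohort 2 dosing, Protocol 4.3 says "the participants will be instructed to take vitamin A palmitate 48,000 IU daily by mouth for one month". SAP 3.1 says "Participants in Cohort 2 will be instructed to take 48,000 IU of vitamin A palmitate daily by mouth from baseline through Month 1". Protocol 8.2 and the SAP 4.0 definition of the treatment completion visit both place the end of supplementation at Month 1 for Cohort 2 and at Month 2 for Cohort 1.

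On safety checks, Protocol 4.3 says of the liver "However, for caution, we will monitor liver function tests", and 4.4.3 calls for headache questions and attention to the optic nerve at every visit. In Appendix 2, Cohort 2 receives supplement at baseline only. The adverse event assessment and the hepatic panel are first scheduled after dosing at Month 1, then at Month 2. The review of systems and the dilated fundus examination follow the same post-dose pattern.

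**The concern.** The count turns on a consequence for treatment (the supplement has to be interrupted or stopped) and not on the reaction itself. That works when a safety check falls while the participant is still dosing. Cohort 1 had such a check at Month 1 of a two-month course. Cohort 2 takes three times the daily dose (48,000 against 16,000 IU) for half as long, and has no scheduled check between baseline and the end of its course.

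Protocol 5.3 lists hepatomegaly and raised intracranial pressure among the effects of vitamin A toxicity. The hepatic panels, fundus examinations and headache questions are the scheduled means of seeing related signs. If what they first show in the higher-dose cohort falls outside the count, the one mandatory report for non-serious reactions stays silent. The information then waits for the semiannual meeting or for someone's discretion, while further participants may be dosed.

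**Working it through.** The plan gives no operating characteristics for this count, so there is no figure to reproduce. The check sets the rule against the calendar, then shows the size under stated assumptions.

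**1. Calendar.** Appendix 2 gives target days of 30, 60 and 90 and a window of ±14 days.

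- Month 1: 30 − 14 = day 16 to 30 + 14 = day 44.
- Month 2: 60 − 14 = day 46 to 60 + 14 = day 74.

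**2. Scheduled post-dose hepatic panels falling before the planned end of dosing, on target days.**

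- Cohort 1 (dosing to Month 2; panels at Months 1, 2 and 3): 1 of 3.
- Cohort 2 (dosing to Month 1; panels at Months 1 and 2): 0 of 2.

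**3. Two readings of when Cohort 2 dosing ends.**

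- *At the Month 1 visit* (Protocol 8.2; SAP 3.1 and 4.0; SAP 8.1.1 also counts expected doses only to the Month 1 date). No dosing remains at any scheduled check. Findings first made there contribute 0 to the count, whether 1 of 5 or 5 of 5 participants are affected.
- *After a fixed course*, taken here as 30 days (an assumption; Protocol 4.3 says one month). Days left at a Month 1 visit on day d are max(0, 30 − d), at two doses a day. Day 16 leaves 14 days (28 of 60 doses), day 25 leaves 5 days (10 doses), day 29 leaves 1 day (2 doses), and day 30 or later leaves none. A finding on days 16 to 29 could therefore require cessation and count.

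**4. Size.** Let p be the true proportion of participants with a non-serious suspected reaction of the kind the rule is meant to count. Let f be the share of those reactions detected while supplement is still being taken. Neither is in the documents, so both are shown as ranges. The number counted is X ~ Binomial(n, p × f), and the table gives P(X ≥ 3). Five participants are planned. Ten is the ceiling with replacements, and because replacements are for participants who leave before one month, n = 10 overstates the number completing a course.

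| n | p | f = 0 | f = 0.25 | f = 0.5 | f = 1 |
|---|---|---|---|---|---|
| 5 | 0.2 | 0 | 0.001 | 0.009 | 0.058 |
| 5 | 0.4 | 0 | 0.009 | 0.058 | 0.317 |
| 5 | 0.6 | 0 | 0.027 | 0.163 | 0.683 |
| 5 | 0.8 | 0 | 0.058 | 0.317 | 0.942 |
| 10 | 0.2 | 0 | 0.012 | 0.070 | 0.322 |
| 10 | 0.4 | 0 | 0.070 | 0.322 | 0.833 |
| 10 | 0.6 | 0 | 0.180 | 0.617 | 0.988 |
| 10 | 0.8 | 0 | 0.322 | 0.833 | 0.9999 |

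The f = 0 column applies to toxicity first found at the scheduled visits when dosing ends at Month 1. The f = 1 column applies when detection after dosing no longer matters. With five participants and p = 0.6, the chance of meeting the count is 0 in the first case and 0.683 in the second.

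**The case against.** A reader might infer that liver or optic-nerve toxicity in Cohort 2 can never count. The documents do not support that. A Month 1 visit on days 16 to 29 can precede the end of a fixed course. Protocol 4.3 also allows visits when clinically indicated, tells participants who cannot tolerate the dose to stop, and requires those on Coumadin to see their prescriber two to four weeks after starting. Reactions found by these routes can count. These points stand, but the early-visit exception rests on an unsettled reading of when dosing ends, and the others are not scheduled liver or optic-nerve checks for every participant. Footnote 9 of Appendix 2, on supplement returned at Month 2, does not show Cohort 2 dosing past Month 1, since Month 2 is Cohort 1's end of treatment.

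Nor is this the plan's only safety criterion. Section 7.1 has a participant-level one (loss of 15 or more letters), any suspected serious reaction can bring the committee together whatever the dosing status, and 13.3 needs no count. Meeting the count obliges only a report; convening stays discretionary. All of this stands and limits the consequence.

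The strongest objection is that semiannual review already does the work. Protocol 4.1 projects five participants in about 12 months. If they are evenly spaced (an assumption), one starts every 12 / 5 = 2.4 months, the third starts at month 4.8 and reaches Month 1 at about 5.8. The count could not be met from scheduled visits sooner, and by then a semiannual meeting is near. But meeting dates are not tied to enrolment, so the wait from month 5.8 to the next meeting could be anything up to six months. The fourth and fifth participants would start at months 7.2 and 9.6, which is 1.4 and 3.8 months later. The benefit is modest, but it is not nil.

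**Conclusion.** The point holds for the planned schedule. As worded, the only study-level count for non-serious suspected reactions would not register toxicity first detected at Cohort 2's Month 1 or Month 2 visits: 0 of 3, even with 5 of 5 participants affected. This rests on dosing ending at the Month 1 visit, as Protocol 8.2 and the SAP have it, or on Month 1 being held on or after day 30 of a fixed 30-day course. The probabilities in the table also depend on assumed values of p and f.

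Two stronger inferences are not supported. One is that Cohort 2 lacks safety oversight: the serious-event route, semiannual review and the general stopping authority all remain. The other is that the wording was overlooked when Cohort 2 was added: the documents do not say how it came about. What remains is more than a missing detail, because a stated safety rule, followed literally, would pass over what the higher-dose cohort's scheduled checks exist to find. It should be corrected.

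**What to change.** Reconcile Protocol 13.2 with 4.3, 8.2 and Appendix 2 on two matters.

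1. Word the Cohort 2 reporting count so that it does not depend on supplement still being taken when the reaction is detected, and so that it can operate on the Month 1 and Month 2 safety checks. Which reactions qualify is for the sponsor's clinicians.
2. State whether Cohort 2 dosing ends at the Month 1 visit or after a fixed course, and carry the answer into SAP 3.1, 4.0 and the expected-dose formula in 8.1.1. This review takes no position on which it should be.

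The cost is a short protocol amendment and any matching SAP edit, with no new visits, tests or committee. The downside is an occasional extra report or committee review. The point does not call for a wait between participants before dispensing. That would be a new dosing rule, and ten courses in sequence at 30 to 44 days each would take 300 to 440 days.

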3.0 PARTICIPANTS

Five participants with AMD who met the eligibility criteria were enrolled into the first cohort. Enrollment for Cohort 1 was halted on May 24, 2019 to focus on enrollment for Cohort 2. For the second cohort, up to five participants with AMD who meet the eligibility criteria may be enrolled in this protocol. Up to five additional participants may be accrued in the second cohort to account for participants who withdraw from the study prior to receiving one month of study supplementation for a reason unrelated to an adverse reaction. Participants in Cohort 1 may enroll

into Cohort 2 as long as their last intake of vitamin A palmitate was greater than two months prior to their enrollment into Cohort 2.

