4.1 Recruitment

Participants will be recruited from the NEI clinic. Participants will be initially recruited from the following protocols: the NEI screening protocol (08-EI-0102), the Ocular Natural History protocol (16-EI-0134), DA Extension (17-EI-0112), Rod Function (16-EI-0024), or DA_AMD (11-EI-0147). Eligibility will be determined by the investigator. The participants must have the presence of one large druse. Self-referral and referral from outside physicians will be permitted. If any recruitment materials are utilized, IRB-approval will be obtained prior to distribution. The projected recruitment time for five participants in the second cohort is approximately 12 months.

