4.4.2 Dosage, Administration, and Storage

For both cohorts, participants are considered to have complied with the protocol if they have consumed at least 80% of the total doses over the treatment period. The first cohort was instructed to take two 8,000 IU pills by mouth once per day (16,000 IU) with a meal. The preliminary analysis of the data from the first cohort shows that 16,000 IU of vitamin A palmitate per day was well tolerated with no adverse events requiring discontinuation of the study product. The data also show that the first cohort did not present significant improvement in dark adaptation after taking 16,000 IU of vitamin A palmitate per day. A higher dose (50,000 IU) has been previously used in other studies of monogenic (inherited) retinal degeneration with good effect and good tolerance.²⁶ It has even been explored in the context of individuals ≥ 50 years old with AMD, albeit a different study design, but the higher dose of vitamin A was well-tolerated.¹⁶ Therefore, for the second cohort, administration of three 8,000 IU pills will occur by mouth twice per day (48,000 IU) and should be taken with a meal. The vitamin A palmitate supplement should be stored at room temperature (15-30°C).

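### Low-cost improvement: Section 13.2 requires notice of non-serious reactions that stop the supplement only at three participants, in practice about three of the planned five at the tripled dose

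*Protocol*

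**What the plan says.** Section 13.2 of the protocol has three relevant routes.

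- **Routine review:** "The Committee will review accumulating data on a semiannual basis to determine whether the study should continue".
- **Suspected serious reactions:** the Clinical Director may assemble the Committee early. No minimum count applies.
- **Non-serious suspected reactions:** the PI must report to the Clinical Director "if three or more participants experience non-serious suspected adverse reactions that require temporary or permanent cessation of the IP". The Clinical Director may then convene the Committee early.

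The third route names no cohort, time window or denominator. Section 13.3 adds that the Committee "may recommend temporarily suspending or closing enrollment or stopping the study at any time due to safety concerns", among other grounds.

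Section 3.0 states that Cohort 1 enrolled five and is closed, and that Cohort 2 plans five. Up to five more may be accrued in Cohort 2, but only to cover those who "withdraw from the study prior to receiving one month of study supplementation for a reason unrelated to an adverse reaction". Section 4.4.2 describes 16,000 IU in Cohort 1 as "well tolerated with no adverse events requiring discontinuation of the study product", on a preliminary analysis, and sets 48,000 IU a day for Cohort 2. Under Section 4.3, participants who cannot tolerate the dose are handled individually: "they will be instructed to stop taking the supplement and they will be removed from the study". Section 4.1 gives the pace: "The projected recruitment time for five participants in the second cohort is approximately 12 months".

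**The concern.** Safety of the dose is part of the stated objective (protocol Section 2.0), and Cohort 2 is where the higher dose is tried. In a group this small, the first reaction that stops treatment is the most informative early sign of poor tolerability. A count of three suits a larger study. Here, if all three cases are in Cohort 2, at most 5 − 3 = 2 of the planned five are still undosed when the duty to notify begins.

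A first or second cessation can wait for the semiannual review as far as 13.2 is concerned. The Clinical Director has the power to act earlier, but 13.2 does not require that he be told. Oversight is meant to be independent of the investigators (Section 13.0), yet under this rule prompt notice of one or two such cases is left to the PI's choice.

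**Working it through.** **Plan's own figure.** The threshold of three has no stated derivation, so there is none to reproduce. The doses check: 2 × 8,000 = 16,000 IU and 3 × 8,000 × 2 = 48,000 IU, a ratio of 3.

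**Effective fraction.** With no case from Cohort 1, the trigger is 3/5 = 60% of the planned Cohort 2. Reaction-related withdrawals are not replaced. The fraction falls to 3/10 = 30% only if all five extra places are used. The Cohort 1 statement covers discontinuation. Temporary stops there are not reported, and any would lower the number needed from Cohort 2.

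**Chance that the trigger is reached.** The inputs are n = 5 dosed (Section 3.0) and a true rate p of non-serious reactions that stop the supplement. The documents give no p, so 5% to 30% is assumed, with participants independent. The formula is P(X = k) = C(5, k) p^k (1 − p)^(5 − k).

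For p = 0.20:
- P(0) = 0.8^5 = 0.328
- P(3 or more) = 10 × 0.008 × 0.64 + 5 × 0.0016 × 0.8 + 0.00032 = 0.058
- P(1 or 2) = 1 − 0.328 − 0.058 = 0.614

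| Assumed p | No cessation | One or two (no ad hoc report required by 13.2) | Three or more (trigger fires) | At least one (a first-case rule reports) | Expected reports, 5p |
|---|---|---|---|---|---|
| 5% | 0.774 | 0.225 | 0.001 | 0.226 | 0.25 |
| 10% | 0.590 | 0.401 | 0.009 | 0.410 | 0.5 |
| 20% | 0.328 | 0.614 | 0.058 | 0.672 | 1.0 |
| 30% | 0.168 | 0.669 | 0.163 | 0.832 | 1.5 |

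With five dosed, an 80% chance of reaching the trigger needs a true rate of about 67%. A first-case rule needs about 28%.

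**Upper bound on exposure.** The SAP (Section 5.1) allows up to ten in Cohort 2. A participant replaced for an unrelated early withdrawal may already have taken the supplement and can count. With ten dosed, the trigger fires with probability 0.070, 0.322 and 0.617 at p = 10%, 20% and 30%. One or two cessations then occur with probability 0.651 − 0.070 = 0.581, 0.893 − 0.322 = 0.571 and 0.972 − 0.617 = 0.355.

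**Further dosing before the next semiannual review.** The pace is 5 participants per 12 months and the longest wait is 6 months, so the maximum is 6 × 5/12 = 2.5. This applies to an early case just after a review. For the average, assume a single cessation, equally likely in any of the five, and a wait uniform over 0 to 6 months. Uncapped further dosing U is then uniform on 0 to 2.5, and the expected number is E[min(U, places left)]:

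- 4 or 3 places left: 2.5/2 = 1.25
- 2 places left: (2²/2)/2.5 + 2 × 0.5/2.5 = 0.8 + 0.4 = 1.20
- 1 place left: (1²/2)/2.5 + 1 × 1.5/2.5 = 0.2 + 0.6 = 0.80
- 0 places left: 0

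The mean is (1.25 + 1.25 + 1.20 + 0.80 + 0)/5 = 0.9.

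**The case against.** The case for leaving the rule alone has substance. The events are non-serious by definition, and suspected serious reactions have their own route. Individuals are protected: those who cannot tolerate the dose stop and leave the study, adverse events and hepatic panels are checked at each follow-up visit, and the study can be stopped at any time. The Clinical Director sits on the Committee and receives the results of the coordinating center's data checks. The protocol also describes about 50,000 IU as well tolerated in AMD, so the lower rates are the more plausible. At 5% to 10%, 59% to 77% of cohorts of five would have no cessation, and the rule would make no difference.

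Slow accrual helps too. One participant every 12/5 = 2.4 months, each dosed for one month, makes dosing nearly sequential. All of this stands, and it limits the size of the point.

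A reader might go further and infer that a first or second cessation would go unreported to anyone outside the study team. The documents do not support that. Section 15.0 sends reportable events to the IRB under Policy 801, Section 6.1 places the study under an IND, and Section 14.0 refers to a monitoring plan. Those texts are not shown and may cover such cases. The claim is confined to what 13.2 itself requires.

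The objection does not remove the gap. Stopping one participant's supplement does not inform those who oversee the rest, and no provision visible in the protocol expressly requires that the Clinical Director be told of a first or second case.

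**Conclusion.** This is a design choice open to cheap improvement, not an error in the plan. Under 13.2 the duty to notify starts at about three of the planned five in Cohort 2, or three of ten at the extreme. With five dosed and assumed rates of 5% to 30%, that point is reached in 0.1% to 16% of cohorts, while 23% to 67% have one or two cessations without an ad hoc report required by this section. With ten dosed, an upper bound, the trigger fires in about 32% at a 20% rate and 62% at 30%.

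These figures rest on assumed rates and on independence between participants. The 0.9 average and 2.5 maximum rest on the projected pace holding. All the probabilities are chances of notice, not of action. They should not be read as participants harmed, nor the three-case rule as a stopping boundary: even when reached, it obliges only a report. Five is the planned size, not a ceiling.

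**What to change.** Add to Section 13.2:

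> For Cohort 2, in place of the three-participant count, the PI shall report to the NEI Clinical Director promptly (e.g., within 7 days of becoming aware, and before the next participant is started where feasible) each participant whose supplement is temporarily or permanently stopped for a suspected adverse reaction, stating the number affected out of the number dosed in Cohort 2. Convening the Committee, pausing or continuing remains at the discretion of the Clinical Director and Committee.

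This sets a deadline, supplies the denominator and settles how the new duty relates to the existing count. It forces no pause and leaves the replacement rules and the analysis unchanged. The cost is a minor amendment with IRB review and one short report per affected participant, at most five in the planned cohort. Some of those reports will concern minor reactions.
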